5. REGISTRATION PROCEDURES

5.1. Screening

Upon signature of consent, screened patient will be entered on study centrally at the Institut Bergonié Coordinating Center by the Study Coordinator.

See procedure of study

5.2. Inclusion

Upon signature of consent, eligible patient will be entered in the study centrally at the Institut Bergonié Coordinating Center by the Study Coordinator.

See procedure of study

6. STUDY TREATMENT

Sponsor will provide Trabectedin and Durvalumab, with identifying labels that will include all the information required by local regulations.

Investigational medicinal products (IMPs) will have to be requested to Institut Bergonié using appropriate forms provided by the Sponsor.

The study sites will have to ensure drug traceability at all times.

6.1. Description of treatment

For instructions regarding drug inventory, handling, reconstitution, dilution, storage, accountability and disposal, please refer to the IMP Investigator's Brochure and/or the more updated Summary of Product Characteristics (SPC), all provided as separate documents.

6.2. Pharmaceutical Informations

Product description	Galenic	Dosage	Route of administration	Storage	Supply
Trabectedin	Infusion	0.05 mg/ml	Intravenous	2°C ≤ temp ≤ 8°C	Yes
Durvalumab	Infusion	50 mg/ml	Intravenous	2°C ≤ temp ≤ 8°C	Yes

6.3. Administration of treatment

Treatment will be administered on an inpatient/outpatient basis.

In a first time, on Day 1, Trabectedin should be administered as a 3-hour intravenous (IV) infusion. All patients must receive corticosteroids e.g. 20 mg of dexamethasone intravenously 30 minutes prior to Trabectedin administration; not only as anti-emetic prophylaxis but also because it appears to provide hepatoprotective effects. Additional anti-emetics may be administered as needed.

Durvalumab should be administered on Day 2 as a 1-hour intravenous (IV) infusion.

Regimen description				
Agent	Dose	Route	Schedule	Cycle Length
Trabectedin	Doses as appropriate for assigned dose level	IV	Day 1	3 weeks
Durvalumab	Fixed doses of 1120 mg	IV	Day 2	

6.4. Durvalumab

6.4.1. Formulation/packaging/storage

Durvalumab will be supplied as a 500-mg vial solution for infusion after dilution. The solution contains 50 mg/mL durvalumab, 26 mM histidine/histidine-hydrochloride, 275 mM trehalose dihydrate, and 0.02% (weight/volume) polysorbate 80; it has a pH of 6.0. The nominal fill volume is 10 mL. Investigational product vials are stored at 2°C to 8°C and must not be frozen. Durvalumab must be used within the individually assigned expiry date on the label.

6.4.2. Study drug preparation

For patients, a fixed doses of 1120 mg should be prepared.

Preparation of durvalumab doses for administration with an IV bag.

The dose of durvalumab for administration must be prepared by the Investigator's or site's designated IP manager using aseptic technique. Total time from needle puncture of the durvalumab vial to the start of administration should not exceed:

24 hours at 2°C to 8°C

4 hours at room temperature

If the final product is stored at both refrigerated and ambient temperatures, the total time must not exceed 24 hours (that is, the individual storage time limits are not additive). If in-use storage time exceeds these limits, a new dose must be prepared from new vials. Infusion solutions must be allowed to equilibrate to room temperature prior to commencement of administration.

No incompatibilities between durvalumab and polyvinylchloride or polyolefin IV bags have been observed. Fixed doses of 1120 mg of Durvalumab for patients will be administered using an IV bag containing 0.9% (w/v) saline with a final durvalumab concentration ranging from 1 to 20 mg/mL, and delivered through an IV administration set with a 0.2- or 0.22-µm in-line filter.

Remove a volume of IV solution from the IV bag equal to the calculated volume of durvalumab to be added to the IV bag prior to addition of durvalumab. Next, the volume of durvalumab is added to the IV bag volume 250 mL (possibility of use IV bag volumes 100 to 1000 mL such that final concentration is within 1 to 20 mg/mL). Mix the bag by gently inverting to ensure homogeneity of the dose in the bag.

Durvalumab will be administered at room temperature (approximately 25°C) by controlled infusion via an infusion pump into a peripheral or central vein. Following preparation of durvalumab, the entire contents of the IV bag should be administered as an IV infusion over approximately 60 minutes (±5 minutes), using a 0.2, or 0.22-µm in-line filter. Less than 55 minutes is considered a deviation.

The IV line will be flushed with a volume of IV solution (0.9% [w/v] saline) equal to the priming volume of the infusion set used after the contents of the IV bag are fully administered, or complete the infusion according to institutional policy to ensure the full dose is administered and document if the line was not flushed.

Standard infusion time is 1 hour. However, if there are interruptions during infusion, the total allowed time should not exceed 8 hours at room temperature. The table below summarizes time allowances and temperatures.

Durvalumab hold and infusion times

Maximum time from needle puncture to start of administration	4 hours at room temperature, 24 hours at 2°C to 8°C
Maximum time for IV bag infusion, including interruptions	8 hours at room temperature

In the event that either preparation time or infusion time exceeds the time limits outlined above, a new dose must be prepared from new vials. Durvalumab does not contain preservatives, and any unused portion must be discarded.

6.4.3. Monitoring of dose administration

Subjects will be monitored before, during and after the infusion with assessment of vital signs at the times specified in the Schedule of Assessment. Subjects are monitored (pulse rate, blood pressure) every 30 minutes during the infusion period (including times where infusion rate is slowed or temporarily stopped).

6.5. Trabectedin

For instructions regarding drug inventory, handling, reconstitution, dilution, storage, accountability and disposal, please refer to the more updated Summary of Product Characteristics (SPC), provided as separate documents.

No lock of the BSA is required.

6.6. General Concomitant Medication and supportive care guidelines

6.6.1. Acceptable concomitant medication

All treatments that the investigator considers necessary for a subject's welfare may be administered at the discretion of the investigator in keeping with the community standards of medical care. All concomitant medication will be recorded on the case report form (CRF). If changes occur during the trial period, documentation of drug dosage, frequency, route, and date may also be included on the CRF.

All concomitant medications received within 28 days before the first dose of trial treatment and 30 days after the last dose of trial treatment should be recorded. Concomitant medications administered 30 days after the last dose of trial treatment should be recorded for SAEs only.

6.6.2. Prohibited concomitant medication

Subjects are prohibited from receiving the following therapies during the screening and treatment phase (including retreatment for post-complete response relapse) of this trial:

- Anti-cancer systemic chemotherapy or biological therapy
- Immunotherapy not specified in this protocol
- Chemotherapy not specified in this protocol
- Investigational agents other than Trabectedin and Durvalumab
- Radiation therapy
 - **Note:** Radiation therapy to a symptomatic solitary lesion or to the brain may be allowed after consultation with Sponsor.
- Live vaccines within 30 days prior to the first dose of trial treatment and while participating in the trial. Examples of live vaccines include, but are not limited to, the following: measles, mumps, rubella, varicella zoster, yellow fever, intranasal influenza, rabies, BCG and typhoid vaccine.
- Systemic glucocorticoids for any purpose other than to modulate symptoms from an event of clinical interest of suspected immunologic etiology

Subjects who, in the assessment by the investigator, require the use of any of the aforementioned treatments for clinical management should be removed from the trial. Subjects may receive other medications that the investigator deems to be medically necessary.

Other medications that are prohibited in this trial are described in the exclusion criteria section.

There are no prohibited therapies during the Post-Treatment Follow-up Phase.

6.6.3. Restrictions during study

6.6.3.1. CONTRACEPTION

The following restrictions apply while the patient is receiving study treatment and for the specified times before and after:

- **Female patient of child-bearing potential:**

Females of childbearing potential who are sexually active with a non-sterilized male partner must use at least 1 **highly** effective method of contraception (table below) from the time of screening and must agree to continue using such precautions for 180 days after the last dose of study treatment. Non-sterilised male partners of a female patient must use male condom plus spermicide throughout this period. Cessation of birth control after this point should be discussed with a responsible physician. Not engaging in sexual activity for the total duration of the drug treatment and the drug washout period is an acceptable practice; however, periodic abstinence, the rhythm method, and the withdrawal method are not acceptable methods of birth control. Female patients should also refrain from breastfeeding throughout this period.

- **Male patients with a female partner of childbearing potential:**

- Non-sterilized males who are sexually active with a female partner of childbearing potential must use a male condom plus spermicide from screening through 180 days after receipt of the final dose of study treatment. Not engaging in sexual activity is an acceptable practice; however, occasional abstinence, the rhythm method, and the withdrawal method are not acceptable methods of contraception. Male patients should refrain from sperm donation throughout this period.
- Female partners (of childbearing potential) of male patients must also use a highly effective method of contraception throughout this period (Table below).

N.B Females of childbearing potential are defined as those who are not surgically sterile (ie, bilateral tubal ligation, bilateral oophorectomy, or complete hysterectomy) or post-menopausal.

Women will be considered post-menopausal if they have been amenorrheic for 12 months without an alternative medical cause. The following age-specific requirements apply:

- Women <50 years of age would be considered post-menopausal if they have been amenorrheic for 12 months or more following cessation of exogenous hormonal treatments and if they have luteinizing hormone and follicle-stimulating hormone levels in the post-menopausal range for the institution or underwent surgical sterilization (bilateral oophorectomy or hysterectomy).
- Women ≥50 years of age would be considered post-menopausal if they have been amenorrheic for 12 months or more following cessation of all exogenous hormonal treatments, had radiation-induced menopause with last menses >1 year ago, had chemotherapy-induced menopause with last menses >1 year ago, or underwent surgical sterilization (bilateral oophorectomy, bilateral salpingectomy or hysterectomy).

Highly effective methods of contraception, defined as one that results in a low failure rate (ie, less than 1% per year) when used consistently and correctly are described in table below. Note that some contraception methods are not considered highly effective (e.g. male or female condom with or without spermicide; female cap, diaphragm, or sponge with or without spermicide; non-copper containing intrauterine device; progestogen-only oral hormonal contraceptive pills where inhibition of ovulation is not the primary mode of action [excluding Cerazette/desogestrel which is considered highly effective]; and triphasic combined oral contraceptive pills).

Table 1. Highly Effective Methods of Contraception (<1% Failure Rate)

• Barrier/Intrauterine methods• Copper T intrauterine device• Levonorgestrel-releasing intrauterine system (e.g., Mirena®)^a	
• Hormonal Methods• Implants: Etonogestrel-releasing implants: e.g. Implanon® or Norplant®• Intravaginal: Ethinylestradiol/etonogestrel-releasing intravaginal devices: e.g. NuvaRing®• Injection: Medroxyprogesterone injection: e.g. Depo-Provera®• Combined Pill: Normal and low dose combined oral contraceptive pill• Patch: Norelgestromin/ethinylestradiol-releasing transdermal system: e.g. Ortho Evra®• Minipill: Progesterone based oral contraceptive pill using desogestrel: Cerazette® is currently the only highly effective progesterone-based
--	--

^a This is also considered a hormonal method

6.6.3.2. BLOOD DONATION

Subjects should not donate blood while participating in this study and for 90 days after receipt of the final dose of investigational products.

6.6.4. Potential drug interaction

6.6.4.1. DURVALUMAB

No formal drug-drug interaction studies have been conducted with durvalumab.

There are no known clinically significant interactions of durvalumab with other medicinal products.

6.6.4.2. TRABECTEDIN

Since Trabectedin is metabolised mainly by CYP3A4:

- Co-administration of trabectedin with potent inhibitors of the isoenzyme CYP3A4 (e.g. oral ketoconazole, fluconazole, ritonavir, clarithromycin or aprepitant) is prohibited.
- Co-administration of trabectedin with potent inducers of the isoenzyme CYP3A4 (e.g. rifampicin, phenobarbital, Saint John's Wort) is prohibited as it would decrease the exposure to trabectedin.

The following website may be referenced for a more extensive list of P450 inhibitors and inducers: <http://medicine.iupui.edu/clinpharm/ddis/main>.

Alcohol consumption must be avoided during treatment with trabectedin due to the hepatotoxicity of the medicinal product. Caution should be taken if **medicinal products associated with hepatotoxicity** are administered concomitantly with trabectedin, since the risk of hepatotoxicity may be increased.

Caution should be taken if medicinal products associated with rhabdomyolysis (e.g. **statins**) are administered concomitantly with trabectedin, since the risk of rhabdomyolysis may be increased.

Concomitant use of trabectedin with **phenytoin** may reduce phenytoin absorption leading to an exacerbation of convulsions. Combination of trabectedin with phenytoin or live attenuated vaccines is not recommended and with yellow fever vaccine is specifically contraindicated.

Concomitant administration of **inhibitors of P-gp**, e.g. cyclosporine and verapamil, may alter trabectedin distribution and/or elimination. The relevance of this interaction e.g. central nervous system (CNS) toxicity has not been established. Caution should be taken in such situations.

6.7. Dosing delays/dose modifications and adverse event management

No changes in durvalumab dose are allowed. If immune related adverse events occur, the durvalumab administration will be adjusted (delayed doses) as per the toxicity management guidelines (Appendix 4).

Dose escalation: Toxicities that would lead to dose modification should be discussed with the sponsor.

Expansion cohorts: Doses will be reduced for haematological and other adverse events. Dose adjustments are to be made according to the greatest degree of toxicity. Adverse events will be graded using the NCI Common Terminology Criteria for Adverse Events Version 4.03 (NI-CTCAE).

6.7.1. General rules for dose modification

6.7.1.1. DURVALUMAB

Management of toxicity is described in appendix 4.

Reactions may occur during or after the infusion of study medication. The reaction may cause fever or chills and a change in blood pressure or difficulty in breathing.

In the event of a \leq Grade 2 infusion-related reaction, the infusion rate of study drug may be decreased by 50% or interrupted until resolution of the event (up to 4 hours) and re-initiated at 50% of the initial rate until completion of the infusion. For subjects with a \leq Grade 2 infusion-related reaction, subsequent infusions may be administered at 50% of the initial rate. Acetaminophen and/or an antihistamine (e.g., diphenhydramine) or equivalent medications per institutional standard may be administered at the discretion of the investigator.

If the infusion-related reaction is Grade 3 or higher in severity, study drug will be discontinued.

The standard infusion time is one hour, however if there are interruptions during infusion, the total allowed time from infusion start to completion of infusion should not exceed 4 hours at room temperature, with maximum total time at room temperature not exceeding 4 hours (otherwise requires new infusion preparation).

As with any antibody, allergic reactions to dose administration are possible. Appropriate drugs and medical equipment to treat acute anaphylactic reactions must be immediately available, and study personnel must be trained to recognize and treat anaphylaxis. The study site must have immediate access to emergency resuscitation teams and equipment in addition to the ability to admit subjects to an intensive care unit if necessary.

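### Protocol 6.4.2 and 6.7.1.1 set incompatible time limits for an interrupted durvalumab infusion, and 6.3 and 6.6.2 conflict on corticosteroid premedication

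*Protocol*

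**What the plan says.** **Infusion time.** Protocol 6.4.2 takes one hour as the standard durvalumab infusion and says that "if there are interruptions during infusion, the total allowed time should not exceed 8 hours at room temperature". Its table repeats the 8-hour figure against the entry "Maximum time for IV bag infusion, including interruptions". The same table has a separate, earlier allowance of up to 4 hours at room temperature between puncturing the vial and starting the infusion.

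Protocol 6.7.1.1 also starts from a one-hour standard. It says that, after interruptions, "the total allowed time from infusion start to completion of infusion should not exceed 4 hours at room temperature", and it adds "with maximum total time at room temperature not exceeding 4 hours (otherwise requires new infusion preparation". For a reaction of grade 2 or lower, the same section lets the infusion be "interrupted until resolution of the event (up to 4 hours) and re-initiated at 50% of the initial rate".

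**Corticosteroids.** Protocol 6.3 says: "All patients must receive corticosteroids e.g. 20 mg of dexamethasone intravenously 30 minutes prior to Trabectedin administration". Protocol 6.6.2 lists, among therapies prohibited during screening and treatment, "Systemic glucocorticoids for any purpose other than to modulate symptoms from an event of clinical interest of suspected immunologic etiology". It adds that subjects who, in the investigator's assessment, "require the use of any of the aforementioned treatments for clinical management should be removed from the trial".

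**The concern.** The two infusion sections address the same event, an interrupted durvalumab bag, and neither is worded to cover a different circumstance. A pharmacist or nurse with a bag that will finish between 4 and 8 hours after the start is told by one section to carry on and by the other to prepare a new one. Section 6.7.1.1 appears to add a second conflict within itself, because the stop it allows is as long as the whole time it allows.

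At stake is consistent handling of a product without preservative. Monitors also need a single rule to judge against, since Protocol 4.5 names incorrect preparation of the medication among deviations that may affect the risk/benefit ratio.

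The corticosteroid texts pose a similar problem of drafting: one section requires what another, read literally, forbids.

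**Working it through.** **Inputs.** Standard infusion 1 hour (6.4.2 and 6.7.1.1). Permitted stop s up to 4 hours, restart at 50% of the initial rate (6.7.1.1). Limits on start-to-completion time: 4 hours (6.7.1.1) and 8 hours (6.4.2). Let f be the fraction of the dose given before the stop. The same bag is assumed throughout.

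**Formula.** The first part takes f hours and the remainder at half rate takes 2(1 − f) hours, so

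T = f + s + 2(1 − f) = 2 − f + s.

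With s = 4, T = 6 − f. The longest stop that fits a 4-hour limit is 4 − (2 − f) = 2 + f. For an 8-hour limit it is 8 − (2 − f) = 6 + f.

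| f | Total with a 4-hour stop (h) | Longest stop within 4 h (h) | Longest stop within 8 h (h) |
|---|---|---|---|
| 0 | 6.00 | 2.00 | 6.00 |
| 0.25 | 5.75 | 2.25 | 6.25 |
| 0.50 | 5.50 | 2.50 | 6.50 |
| 0.75 | 5.25 | 2.75 | 6.75 |
| near 1 | just over 5 | just under 3 | just under 7 |

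Three results follow.

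- A full 4-hour stop always breaks the 4-hour limit and always meets the 8-hour one.
- The sections disagree for any stop longer than 2 + f hours, up to the permitted 4.
- Slowing to half rate without a stop takes 2 − f hours, at most 2, and meets both limits. The conflict therefore does not arise from a rate reduction alone.

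**Room-temperature time.** Read literally, 6.4.2 permits 4 hours before the start plus 8 hours of infusion, so 4 + 8 = 12 hours, against a total of 4 hours in 6.7.1.1. If that total is taken to include time before the start, each such hour shortens the usable stop by an hour.

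**Appendix 4.** Its table on infusion-related reactions allows a temporary interruption until the event resolves and gives no duration, so it does not settle the matter.

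**Corticosteroids.** No arithmetic applies. Section 6.3 is mandatory for all patients and gives intravenous dexamethasone as its example, which is a systemic glucocorticoid. Section 6.6.2 has one exception, for events of suspected immune origin, and premedication is not among them. Section 6.6.1 gives the investigator general latitude over concomitant treatment but does not lift the specific prohibition. As written, giving the premedication departs from 6.6.2 and omitting it departs from 6.3.

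**The case against.** **On the infusion.** The stop is a maximum, and 6.7.1.1 supplies a remedy once its limit is passed: a new preparation. A long stop could be followed by a restart from a fresh bag, so the 5 to 6 hours holds only if the same bag is used. That stands, and it makes the conflict inside 6.7.1.1 conditional on the same bag. It does not remove the conflict between sections: for a bag finishing between 4 and 8 hours, 6.4.2 keeps it and 6.7.1.1 replaces it.

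**On corticosteroids.** The list in 6.6.2 concerns concomitant medication. Its first item, anticancer chemotherapy or biological therapy, carries no exemption for protocol treatment, so read equally literally it would forbid the study drugs. The list was evidently not written with protocol-mandated treatment in mind. This stands as a reason to expect sites to follow 6.3, but the written conflict remains.

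Three stronger inferences are tempting, and the documents do not support them.

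- *The time limit alters cycle-1 durvalumab dose intensity, and so DLT evaluability.* SAP 2.3 does exclude patients at or below 75% relative dose intensity because of a drug-related event that is not a DLT. But both infusion sections call for a new preparation when time runs out, and Protocol 6.7 allows no change in durvalumab dose. Nothing links the 4-hour or 8-hour limit to a reduced dose.
- *Every patient must be removed.* Removal in 6.6.2 depends on the investigator's assessment that an individual needs a prohibited treatment for clinical management. Premedication required of everyone is not such an assessment.
- *Day-1 premedication breaches exclusion criterion 2, whose 21-day window runs to the first durvalumab dose on day 2.* That criterion is judged before treatment starts, and SAP 2.2.3 records it as an investigator decision on the eligibility form. Later premedication does not make an included patient ineligible.

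**Conclusion.** The infusion limits are wrong as written: 8 hours against 4 for the same interrupted bag, plus a permitted 4-hour stop that, with that bag, leads to 5 to 6 hours in total. At most 2 to 3 hours of the stop can be used under the 4-hour limit. This rests on the one-hour standard infusion, half-rate restart and no change of bag. It affects only interrupted or prolonged infusions, and the consequence is whether a bag is used or re-prepared.

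The corticosteroid conflict is real in the text and lesser in practice, since sites would probably give the premedication. It supports neither mass removal nor ineligibility.

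Neither point changes a sample size, an error rate or an analysis population. Both are worth correcting because they bear on safety and are cheap to resolve.

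**What to change.** The sponsor should reconcile Protocol 6.4.2 (text and table) with 6.7.1.1, so that there is one maximum infusion time and one maximum room-temperature time. The protocol should state whether time before the start counts towards the latter, and the permitted interruption should be consistent with both, with a statement of when a new preparation is needed.

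It should also reconcile 6.3 with 6.6.2, so that the protocol's own premedication has one stated status.

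No view is taken on which limit or rule is right. The cost is a protocol clarification, with no effect on the sample size or the planned analyses.
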